2.2 Secondary objective

To evaluate the efficacy of everolimus on neurocognition and behavior in individuals with PTEN mutations compared to placebo as measured by standardized, direct and indirect neurocognitive tools and behavioral measures. The main efficacy endpoint will be a composite index score of neurocognitive function that will be computed in two ways. The first will be an average of measures evaluating working memory (Stanford-Binet Intelligence Scales, Fifth Edition; SB-5 working memory subscale), processing speed (Conners' Continuous Performance Test, Third Edition; CPT-3 mean reaction time), and fine motor skills (Purdue Pegboard Test average of both hands). The second will include the above average weighted by two-thirds and an average of the remaining standardized, norm-referenced neurocognitive measures (e.g., non-verbal ability, visuomotor skills, verbal learning, receptive and expressive language) weighted by one-third. We hypothesize that individuals receiving everolimus will show more improvement, relative to those taking placebo, in the composite index.

Additional efficacy endpoints will examine the effect of everolimus on overall global clinical improvement, autism symptoms, other behavior problems, and adaptive abilities as measured by validated, standardized instruments including the Clinical Global Impressions-Improvement scale, Autism Diagnostic Observation Schedule – Second Edition (ADOS-2 calibrated severity score), Social Responsiveness Scale - Second Edition (SRS-2), Adult/Child Behavior Checklist (CBCL ACF/CBCL), Wide Range Assessment of Memory and Learning, Second Edition (WRAML-2), and Vineland Adaptive Behavior Scales, Third Edition (VABS-III). We will also assess the effect of everolimus treatment on eye tracking tasks, resting state EEG, and task related EEG through auditory evoked potentials (AEP).

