AEP Procedures: Auditory evoked potentials will be collected using the same EEG system as the resting EEG, with clicks as the auditory input. Subjects will passively listen to 150 sets of two 5 ms broadband noise bursts (65 db) separated by an inter-stimulus interval of 500 ms with inter-set intervals of 4,000 ms (total duration=~12 mins). Offline, data will be average referenced and filtered for time-frequency analyses.

EEG/AEP data from the three sites will be transferred and analyzed by [name]. The data will be transferred from CCF and Stanford to Boston by using Children's Hospital Boston File Transfer (CHBFT). This system has been approved by the IRB for use of secure file transferring. Once transferred, data will be stored at BCH on a password-encrypted computer and only research staff will have access to the files.

Along with the EEG/AEP data, photographs will be taken of the electrode placements on participants' head. These photos will allow the research staff to view electrode placement and make informed decisions concerning poor data in relation to incorrect electrode placement. Participants will also be videotaped during the EEG and AEP procedures. By videotaping participants, researchers will be able to determine whether abnormal EEG data may be due to the participant's behavior. The photographs and videos will allow the research staff to ensure appropriate collection methods are used. Both the photographs and the videos that are collected will be sent to [name] at Boston Children's Hospital via secure methods. This data will be stored on securely at the DMCC.

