For analysis of AEP data, data will be epoched into 2000 ms trials (-500 to 1500 ms), and baseline corrected using the 500 ms period prior to the first auditory stimulus in each trial. Any trial with amplitude exceeding 150 uV will be removed. N1 will be defined as the most negative-going waveform deflection between 50 and 150ms post-stimulus, over the central region. (If N1 cannot be adequately identified in this population using these criteria, independent components analysis will be used to identify the N1 component instead). Habituation of the N1 amplitude will be quantified as percent change from the first to second auditory click in each trial. Intertrial phase coherence (ITPC) will be calculated using the function *newtimef*, and reported as the maximum absolute value ITPC in the 50-150ms timeframe, in the alpha frequency band (8-12Hz).

Two approaches will be used to explore whether changes in PTEN-pathway molecules are correlated with changes in clinical improvement. First, we will use the mixed effects modeling framework to examine the correlation between the longitudinal changes in the neurocognitive composite score and changes in PTEN-associated pathway molecules. In this framework, the relationship between slopes representing individual clinical changes and individual PTEN-pathway molecule changes are estimated. We will also examine whether this correlation differs by treatment group. Second, we will estimate a structural model with cross-lagged relationships estimated between screening/3-month PTEN-pathway levels and 3-month/6-month efficacy measurements. Rather than evaluating the relationship between changes over time, the cross-lagged structural model examines whether pathway molecule levels at earlier time points predict efficacy measurements at later time points. Each of these methods will use all available data following the intent-to-treat principle. As a result, they are less likely to produced biased estimates than a bivariate correlation approach using changes from baseline because the latter method can only be computed for individuals with complete data.

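### As worded, N1 habituation is a percent change within each single epoch with no averaging step, and inter-trial phase coherence is not protected against differing numbers of clean trials

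*Combined protocol and SAP*

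**What the plan says.** Section 2.2 brings the electrophysiology into the treatment comparison: "We will also assess the effect of everolimus treatment on eye tracking tasks, resting state EEG, and task related EEG", the last of these through auditory evoked potentials (AEP). Section 7.12 gives the stimulus ("Subjects will passively listen to 150 sets of two 5 ms broadband noise bursts") and makes the procedure optional at baseline, 3 months and 6 months.

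Section 17 names three EEG/AEP outcomes: gamma power, N1 habituation and phase locking. The AEP steps are:

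- Segmentation: "data will be epoched into 2000 ms trials (-500 to 1500 ms", each corrected to its own pre-click baseline.
- Rejection: "Any trial with amplitude exceeding 150 uV will be removed".
- Peak: "N1 will be defined as the most negative-going waveform deflection between 50 and 150ms post-stimulus, over the central region".
- Habituation: "Habituation of the N1 amplitude will be quantified as percent change from the first to second auditory click in each trial".
- Phase locking: inter-trial phase coherence (ITPC), "reported as the maximum absolute value ITPC in the 50-150ms timeframe", in the 8–12 Hz band.

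No AEP step averages epochs before the peak is picked. No rule turns the per-epoch values into one value per patient and visit. ITPC has no minimum number of clean trials, no matching of counts and no bias correction. For resting EEG, by contrast, the same section does specify averaging the power spectrum over epochs.

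**The concern.** Within the AEP paragraph a trial is the unit that is segmented, baseline-corrected and rejected, so it is one epoch with one click pair. A percent change taken in each trial is then a ratio of two single-epoch peaks. Two things go wrong with such a ratio. Choosing the lowest point of a noisy 100 ms window pushes both peaks down, which pulls the ratio towards no change. And some first-click peaks lie near or above zero, so dividing by them gives extreme values that dominate a mean.

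ITPC has a different problem. It is the length of a mean of unit vectors, so it is positive even when phases are random, and more so with fewer trials. Recordings that lose more epochs to the amplitude rule will read higher for that reason alone.

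Two of the three named EEG/AEP outcomes are affected. Section 7.12 values these paradigms as possible future biomarkers of treatment response and knows of no earlier quantitative EEG or AEP work in PTEN, so there is no PTEN data set against which a weak measure would stand out.

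**Working it through.** **Inputs from the documents.** There are 150 click pairs, 500 ms between the clicks of a pair, and "inter-set intervals of 4,000 ms (total duration=~12 mins". Clicks at 0 and 500 ms put the two N1 windows at 50–150 and 550–650 ms, both inside one epoch of −500 to 1500 ms. Duration check: 150 × (0.5 + 4.0) s = 675 s = 11.25 min, consistent with the stated figure. So a recording yields at most 150 trials, one pair in each.

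**Inputs assumed.** The documents give no N1 amplitude, noise level, clean-trial yield or true ITPC, and no precision or power for either measure, so there is no planned figure to reproduce. Ranges are used instead.

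**N1 habituation.** Two-second epochs were simulated with 1/f noise, a true change of −40%, 120 clean epochs, the planned baseline and the planned peak rule, 200 runs per setting. With peaks p1 and p2, the measure is 100 × (p2 − p1)/p1, taken per epoch or once on the averaged waveform.

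| N1 (µV) | Noise SD (µV) | Mean of per-epoch changes: median (IQR) over runs | Median over epochs | Averaged waveform (SD) |
|---|---|---|---|---|
| 3 | 5 | +15 (−20, 55) | −14 | −37 (15) |
| 3 | 15 | +13 (−43, 65) | −13 | −8 (71) |
| 5 | 5 | +14 (−12, 34) | −15 | −37 (11) |
| 5 | 10 | +7 (−27, 51) | −13 | −35 (18) |
| 5 | 15 | +25 (−26, 66) | −13 | −28 (36) |
| 8 | 5 | 0 (−13, 13) | −21 | −39 (7) |
| 8 | 15 | +12 (−27, 55) | −13 | −34 (18) |

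Across all settings, 0.7% to 5.6% of first-click peaks were at or above zero. The attenuation of the median follows from peak picking: with N1 of 5 and 3 µV, adding the same c to both peaks gives −200/(5 + c), which equals −13% at c ≈ 10.4 µV.

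In a further run, true habituation varied between patients with an assumed SD of 20 points. Over the amplitude and noise settings tried, the mean of per-epoch changes explained 0.00–0.01 of that variance and the median over epochs 0.05–0.73. The averaged waveform explained 0.25–0.89.

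A second simulation with true −50%, N1 5–8 µV and noise SD 3–15 µV gave −27% to +17% for the per-epoch mean, about −14% to −35% for the median over epochs, and about −38% to −50% for the averaged waveform.

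**ITPC at one time-frequency point, no locking.** The mean is √(π/(4N)):

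- N = 150: √0.00524 = .072
- N = 50: √0.01571 = .125
- N = 30: √0.02618 = .162

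**ITPC as planned**, the maximum over 50–150 ms and 8–12 Hz (simulated with 3-cycle wavelets):

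| Response (value at 1000 trials) | 150 | 100 | 50 | 30 |
|---|---|---|---|---|
| none (.047) | .126 | .152 | .217 | .277 |
| weak (.192) | .218 | .230 | .282 | .326 |
| moderate (.307) | .326 | .332 | .376 | .406 |
| strong (.463) | .479 | .481 | .505 | .540 |

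Going from 150 to 50 trials shifts a weak response by .282 − .218 = .064 and a strong one by .505 − .479 = .026. Against simulated SDs of .056 and .058 at 100 trials, that is 1.1 and 0.4 SD. Those SDs hold the true response fixed, so real between-patient spread would make the standardised shift smaller. A milder gap, 150 against 100 trials, shifts ITPC by .481 − .479 = .002 (strong) to .152 − .126 = .026 (none).

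**The case against.** The best defence on N1 is that the single-epoch reading is literal but not the only one. The same paragraph uses *in each trial* for the baseline period simply to say which click is meant, so the habituation sentence may only be identifying the two clicks of a pair. Section 7.12 describes the target as an event-related potential response, which would ordinarily be an average. If averaging was intended, the fault is one of wording. This stands, but the plan does not say so.

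A reader might go further and infer that the habituation outcome is mostly noise, or unusable. The documents do not support that. They give no signal-to-noise values and do not say that per-epoch values would be combined by a mean. A median over epochs is attenuated but can still carry information.

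A reader might also infer that a drug effect on restlessness would pass for an effect on phase locking. Nothing in the documents says everolimus changes trial loss, and the comparison is randomised and blinded. Section 17 adds automated artefact removal and an independent-components fallback for N1, and Section 7.12 adds video and electrode photographs. None of these equalises trial counts, but the bias enters the arm comparison only if counts differ by arm.

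In the other direction, the single-point formula might suggest that the bias is negligible once locking is moderate. For the planned maximum it is not: .326 at 150 trials against .406 at 30.

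Finally, the stakes are low. The recordings are optional, Section 3.5 treats them as exploratory, Table 12 omits them, and Section 17 describes the analyses as mainly descriptive. The data are stored, so both measures could be recomputed.

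**Conclusion.** The concern holds as a gap in specification. On the literal wording, N1 habituation is formed within single epochs, with no averaging and no rule for combining them. Under the assumed amplitudes and noise levels, a mean of those values is strongly attenuated or has the wrong sign, and a median is attenuated. The averaged waveform comes much closer to the truth at most settings but loses precision as noise rises, and at N1 3 µV with noise SD 15 µV it too fails (−8% against −40%, SD 71 points).

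The ITPC bias does not rest on a reading of the text: ITPC rises as clean trials fall, and taking the maximum enlarges the effect. Its consequence is extra variance, or a visit trend if counts change over visits. Bias between arms needs a difference in clean-trial counts between arms, which the documents neither predict nor rule out.

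The safety endpoint and the neurocognitive composite are untouched. This is a worthwhile clarification of an optional outcome and does not threaten the trial's conclusions.

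**What to change.** Two changes to the AEP paragraph of Section 17:

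1. **N1.** For each patient and visit, average the artefact-free epochs, measure N1 to click 1 and click 2 on that average, then compute the percent change. Report the difference in µV as well, since it does not depend on a possibly small denominator.
2. **ITPC.** Use a measure whose expectation does not depend on trial count, such as pairwise phase consistency, or subsample every recording to one common number of clean trials. In either case report clean-trial counts by arm and visit.

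The cost is analysis work only; no new data or visits are needed. Subsampling discards trials and may drop or flag short recordings in an optional subset of at most 40 patients, which favours the pairwise measure. The averaged N1 measure will still be imprecise in noisy recordings.

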17.1 Power Estimation

This is the first study to evaluate the efficacy of everolimus in patients with a PTEN mutation and ASD/DD. As such, analyses will be predominantly descriptive with the intent of generating plausible hypotheses to be tested in a Phase III confirmatory trial. The planned recruitment sample size of 40 was based on three considerations: 1) the expected recruitment potential of the three sites, 2) a desire to ensure sensitivity to any enrichment in side effects or problems with tolerability in everolimus treated patients, and 3) the need for adequate statistical power in examining primary and secondary efficacy outcomes. Assuming an overall dropout rate of approximately 10%, 44 patients will need to be enrolled to get 40 patients with complete trial data. However, following intent to treat procedures, all patients who are randomized, dosed, and for whom baseline data is collected will be included in statistical analyses. Statistical power considerations for each aim/hypothesis are described below. Except for safety analyses, where only everolimus-treated patients would be expected to show enrichment of dropout or side effects, statistical power estimates are based on one-tailed significance tests with Type 1 error rate of α =.05.

Primary Objective- Safety. The planned sample size of 40 is underpowered to detect small differences in dropout rates or side effects between everolimus versus placebo-treated groups. Statistical power will only be adequate if at least a 35% difference in the proportion of dropout/side effects is observed (1- β ≥.81), assuming a one-tailed Type 1 error rate of α =.05. This is equivalent to 1/20 patients experiencing an adverse event/side effect in the placebo arm and 8/20 in the treated arm. Similarly, statistical power of survival analyses will only be fair (1- β ≥.57) if a hazard ratio of 7.5 is observed, equivalent to a 5% dropout rate in the placebo group versus a 30% dropout rate in the everolimus group. However, because the goal is to maintain sensitivity to any potential enrichment in dropout or side effects, any indicator showing a difference of 10% or greater will be considered a meaningful difference and will be reported.

Secondary Objective – Efficacy. For power estimation purposes, the variability in PTEN patients treated with an mTOR inhibitor is expected to be similar to the untreated sample. Preliminary data indicates that the measures which comprise the dominant portion of the neurocognitive composite index (processing speed working memory, and fine motor) are highly sensitive to the brain dysfunction seen in PTEN patients with ASD. The effect sizes are approximately 1 SD or larger. In a comparison between mTOR treated vs. untreated PTEN patients, an effect size of at least 0.65 SD would be of interest and represent clinically- meaningful improvement. For example, an effect size of at least 0.65 SD on cognitive measures would translate to a 10-point standard score improvement in the everolimus-treated group relative to placebo. An improvement of 10 or more points is outside the standard error of measurement for most cognitive measures and is typically considered a reliable change when disordered populations are re-tested.

A sample size of 40 (20 per arm) patients will permit detection of endpoint (6-month follow-up) differences of at least 0.80 SD at the 5% significance level (one-sided alpha = 0.05) with 80% power (1- β). Statistical power will be weaker (1- β =.65) if smaller cross-sectional differences are observed (0.65 SD). However, statistical power is very strong, even for smaller differences (Cohen's d≥.50 equivalent to ≥.50 SD difference) when the full repeated measures nature of the design is considered – baseline, 3-month follow-up, 6-month follow-up. Assuming even modest correlations between repeated measurements of outcome variables (r≥.30), power to detect clinically meaningful differences of .50 SD is very good (1- β =.83; one-sided α =.05). If the primary outcome measure (neurocognitive composite) meets nominal statistical significance in the expected direction (one-tailed p<.05) or a secondary outcome measure meets a more stringent false discovery rate-corrected

significance level in the expected direction, these outcomes will be considered candidates for Phase III confirmatory trial evaluation. To determine if a secondary outcome meets the more stringent false discovery rate-corrected significance level, a Benjamini-Hochberg false discovery rate correction will be applied with adjustment for all secondary outcome measures. This adjustment involves sorting the list of obtained p-values in descending order. The smallest p-value is then compared to the most stringent alpha, the next smallest is compared to the next most stringent alpha, and so on. Only those secondary outcomes meeting FDR-corrected alpha level will be considered candidates for Phase III evaluation.

An interim analysis will be conducted after half the sample has been collected (10 patients in each arm) and will mainly focus on safety. Efficacy interim analysis may be under-powered, but will focus on whether the effects are in the expected direction and whether effect sizes (both the endpoint effect size and the interaction fully utilizing repeated measures) are approaching expected levels (at least Cohen's d≥.30). The goal of the interim analysis for efficacy will be to get a signal that will allow us to design more targeted trials in the future. As such, we will check for a signal in any domain and, if needed, include additional endpoints before the end of the study to expand the endpoint and optimize outcome.

Additional considerations. This is the first clinical trial in patients with PTEN mutations and ASD/DD. For this reason, and to facilitate recruitment, all types of PTEN mutations will be permitted within the randomized patients. However, post-hoc analyses will be completed to examine the existence of any differential effect of treatment based on the type of PTEN mutation (missense vs. other mutation types) or mutation location (exon number, location in 3-D PTEN structure).

18. Protocol Amendments or Changes in Study Conduct

Any change or addition (excluding administrative) to this protocol requires a written protocol amendment that must be reviewed by the central IRB at Boston Children's Hospital (Boston and Stanford only), Cleveland Clinic IRB the NIH, and Novartis as applicable. Amendments significantly affecting the safety of subjects, the scope of the investigation or the scientific quality of the study require additional approval by the IRB at each study center. A copy of the written approval of the IRB must be provided to Novartis.

Examples of amendments requiring such approval are:

- 1. increases in drug dose or duration of exposure of subjects.
- 2. significant changes in the study design (e.g. addition or deletion of a control group),
- 3. increases in the number of invasive procedures,
- 4. addition or deletions of a test procedure required for monitoring of safety.

These requirements for approval should in no way prevent any immediate action from being taken by the investigator or by Novartis in the interests of preserving the safety of all patients included in the trial. If an immediate change to the protocol is felt to be necessary by the investigator and is implemented for safety reasons Novartis must be notified and the IRB at the center must be informed immediately. Amendments affecting only administrative aspects of the study do not require formal protocol amendments or IRB approval but the IRB must be kept informed of such administrative changes. Examples of administrative changes not requiring formal protocol amendments and IRB approval include:

- 1. changes in the staff used to monitor trials
- 2. minor changes in the packaging or labeling of study drug.

19. Compensation

As a part of this study we may be able to provide travel reimbursement (i.e. airfare, hotel, and mileage costs) and/ or parking and meal vouchers for participants. The reimbursement process at Boston Children's Hospital and Stanford University will go through the National Organization for Rare Disorders (NORD). NORD will provide reimbursements in the form of a check to families after they have completed the study visit. The study team at Cleveland Clinic will reimburse their participants directly. Participants/families can receive up to \$1,500 per completed study visit.

20. Privacy Provisions

To maintain the privacy of potential subjects, they will only be approached regarding study enrollment as part of their routine clinical care or via a mailed letter that they may choose to response to. Individuals will not be approached by someone they do not know or anticipate in an unknown or unwanted environment. Data and identifying information collected as part of this study will only be released to those listed in the consent/assent forms.

21. Confidentiality Provisions

Subjects will be provided with a unique ID code and only the study coordinator, Principal Investigator and study monitor will be able to view the link between participants' names and the unique ID. The link to all codes will be maintained in a secure, HIPAA compliant database in the study coordinator's office. The unique patient number will be used on all research documents, including case report forms, as well as on labels on samples collected. All information from this study will be kept in the same research binder in the study coordinator's private and locked office. This will include all paperwork with identifying information, including tracking sheets, orders, consents, etc.

Subject confidentiality will be maintained by the investigator, the investigator's associates and co-workers, and by all administrators who are part of the project. Confidentiality will be maintained according to ICH E6; 4.8.10, part O: "Records identifying the subject will be kept confidential and, to the extent permitted by the applicable laws and/or regulations, will not be made publicly available. If the results of the trial are published, the subject's identity will remain confidential."

The investigator, his or her staff and associates, and the appropriate regulatory agencies may use the information included in this protocol as necessary for the conduct of the trial and the safety of subjects. The parent/guardian/subject may obtain the results of clinical and procedures obtained for this research study if (1) results are available and (2) disclosure does not have the potential to impact the accuracy of future assessments of the subject during the course of the study.

Data file records that are to be shared between sites will be encrypted before sharing so that they will be undecipherable if intercepted in transit. All subject data entered into the study database will be identified only by a unique identifier for research records. Publications will reflect only unique identifiers. Data on paper will be kept locked. Any data on computer will be accessible only by password access. Only members of the research team will have access to these files.

In addition, data will be placed into one or more publicly-accessible scientific databases. For example, the National Institutes of Health maintained databases called the database of Genotypes and Phenotypes (dbGaP) and the National Database for Autism Research (NDAR).

Data from this study will be submitted to the National Database for Autism Research (NDAR). NDAR is a computer system run by the National Institutes of Health that allows researchers studying autism to collect and share information with each other. With an easier way to share, researchers hope to learn new and important things about autism more quickly than before.

During and after the study, the researchers will send information obtained about the subject's health, behavior and genetics information to NDAR and/or submit to other publicly-accessible scientific databases. However, before the information is sent, the researchers will remove information such as name, address, and phone number, and replace that information with a code number. Other researchers nationwide can then file an application with the National Institutes of Health to obtain access to the study data for research purposes. Experts at the National Institutes of Health who know how to protect health and science information will look at every request carefully to minimize risks to subject privacy.

